1.0 Objectives

1.1 Describe the purpose, specific aims, or objectives of this research.

Response: To study the effects of liraglutide (a drug used to treat type 2 diabetes) on glucose (sugar) control over the 26 week study period when used in addition to insulin. The use of Liraglutide in Type 1 Diabetes is investigational

1.2 Describe the purpose, specific aims, or objectives.

Response:

Aim 1.1: To compare the mean HbA1c, fasting glucose, weekly glucose, the standard deviation of weekly blood glucose concentrations as recorded by continuous glucose monitoring, fructosamine and the dose of insulin required prior to and following 26 weeks of treatment with liraglutide.

Aim 1.2: To compare the postprandial glucose concentrations following a test meal before and after 26 weeks of treatment with liraglutide.

Aim 2.1: To compare the basal and postprandial glucagon and C-peptide concentrations following a test meal before and after 26 weeks of treatment with liraglutide.

Aim 3.1: To compare ROS generation, TBARS, intranuclear NF κ B binding in MNC, the expression of TLR-4, TNF α , I κ B α , MMP-9, SOCS-3, PKC β II, PTP-1B, GSK-3 β , IKK β , JNK-1, I κ B and pI κ B in MNC and adipose tissue and plasma concentrations of CRP, MCP-1, PAI-1, TNF α , RANTES, free fatty acids (FFA) prior to and following: a) a single injection of liraglutide 1.2mg at first study visit; b) treatment with liraglutide for 26 weeks.

Aim 3.2: To compare the changes in NF κ B binding and the expression of TLR-4, TNF α , I κ B α , SOCS-3, PTP-1B, PKC β II, IKK β and JNK-1 in MNC following a standard meal challenge prior to and after 26 weeks of treatment with liraglutide..

Aim 4.1: To assess subcutaneous fat mass, hepatic fat content and visceral fat mass by MRI of abdomen and DEXA before and 26 weeks after treatment with liraglutide.

Aim 4.2: To assess change in waist circumference, blood pressure, triglycerides, HDL cholesterol and incidence of metabolic syndrome after treatment with liraglutide

Aim 5.1: To compare the gastric emptying as measured by acetaminophen absorption before and 26 weeks after treatment with daily subcutaneous liraglutide injection.

Aim 6.1: To compare the blood pressure using a 24 hour blood pressure monitor before and 26 weeks after treatment with liraglutide.

Aim 6.2: To compare endothelial function by measuring flow mediated dilatation (FMD) in brachial artery before and 26 weeks after treatment with liraglutide.

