Study visit day -7: Meal challenge test: In order to assess the changes induced by liraglutide, a meal challenge will be carried out prior to and following liraglutide (week 0 and week 26): a 910 calorie high fat high carbohydrate meal will be given, as in several of our previous papers(20).Bolus dose will be given at 3-4 hours after the ingestion of the meal based on the blood sugar and correction factor for each individual subject as giving bolus insulin immediately before meal may confound the true effects of liraglutide. Acetaminophen (1000 mg for body weight <125lbs, 1250 mg for body weight 125-150 lbs, 1500 mg for body weight 151-175 lbs and 1750 mg for body weight >175 lbs) will be ingested at the beginning of the meal, and the blood levels of acetaminophen will be determined at intervals for assessment of the rate of gastric emptying. Liraglutide will be injected only at week 26 (45 min prior to the meal). Sequential blood samples will be obtained at 0, 15, 30, 45, 60, 90, 120, 150, 180, 210, 240 and 300 min. Samples at 15, 30, 45, 90, 150 and 210 min will be 5 ml while those at 0, 60, 120, 180, 240 and 300 min will be 30 ml (total volume=210 ml). Blood will be collected from an indwelling intravenous canula in a superficial forearm vein.

Study visit day -1: Subjects will come fasting for this visit. Records of blood glucose concentrations monitored by fingerstick and CGM for the previous 14 days will be obtained to assess their glycemic control prior to liraglutide treatment (**this will serve as the baseline assessment of mean blood glucose for the study**). The subjects will have their 24 hour blood pressure measurements completed. Brachial reactivity will be assessed by measuring by flow mediated dilation (FMD). They will undergo a meal challenge test (described below) and a fat biopsy. 24 hr urine will be collected.

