Study Visit day 0: Subjects will come fasting for this visit. Each subject will be given one injection of Liraglutide 1.2 mg or placebo. A fructosamine and blood samples will be collected at baseline. Blood samples will be collected after the baseline at 30, 60, 120, 180, 240 and 300 minutes after the injection. (**This is being done to evaluate the acute effect of a single injection of Liraglutide on oxidative stress and inflammatory mediators, before any adjustments of insulin dose or effect of Liraglutide on blood glucose and weight is evident**). Subjects will be instructed by the study staff in the dosing and administration of the study medication. They will start Liraglutide injection at a dose of 0.6 mg per day or placebo injection on the following day. We will adjust the doses of basal and bolus insulin to eliminate low blood sugars(less than 70 mg/dl). At all subsequent visits insulin doses will be titrated to target blood sugars between 70-180 mg/dl at all times. Patients will return to the center after 7 days.

Study Visit week 1: Blood glucose concentrations will be reviewed. Insulin dose will be adjusted at the discretion of the study investigator to optimize blood sugar control as per

the targets mentioned above. Patients will be advised to increase the Liraglutide dose to 1.2 mg a day if they are able to tolerate the 0.6 mg dose. If they are experiencing mild nausea, subjects will continue with 0.6 mg daily for another 7 days. Those with severe nausea/vomiting will be dropped from the study. All other subjects will return in 7 days.

Study Visit week 2: Blood glucose concentrations will be reviewed. Insulin dose will be adjusted if needed. Subjects taking 0.6 mg dose and experiencing significant nausea will be dropped from the study. Subjects on 1.2 mg and experiencing significant nausea will decrease the dose to 0.6 mg and continue that dose for the duration of the study. Subjects on 1.2mg and experiencing mild nausea will continue on 1.2 mg for 2 more weeks. Subjects on Liraglutide 1.2mg daily without any gastro-intestinal side-effects will be asked to increase the dose to 1.8 mg daily. Study drug will be dispensed for additional 2 weeks.

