Study Visit week 4: Subjects will be asked to bring in their used study pens and the pen that they are using so that study nurse can log in the amount of drug used. If needed, the dose will be increased. The goal in the first 4 weeks is to increase patient's liraglutide dose to maximum tolerated dose. Maximum dose of liraglutide will be 1.8 mg daily. Subjects experiencing mild nausea with 0.6 mg or 1.2 mg will continue at that dose in the study. Those with severe nausea/vomiting with 1.8mg will decrease their dose to 1.2 mg and continue that dose throughout the study. Blood glucose concentrations will be reviewed. Insulin dose will be adjusted if needed. CGM will be discontinued. Study drug will be dispensed to last till the next visit.

Study visit week 8: Subjects will be asked to bring in their used study pens and the pen that they are using so that study nurse can log in the amount of drug used. Blood glucose concentrations will be reviewed. Insulin dose will be adjusted if needed. Study drug will be dispensed to last till the next visit.

Study Visit week 12: Subjects will be asked to bring in their used study pens and the pen that they are using so that study nurse can log in the amount of drug used. Blood glucose concentrations will be reviewed and vascular activity will be performed. Insulin dose will be adjusted if needed. Fasting blood, research labs, HbA1c, fructosamine, lipid panel, urine pregnancy test and 24 hr urine will be collected. FMD and 24hr blood pressure will be studied. Study drug will be dispensed for additional 4 weeks.

Study Visit week 16 and 20: Subjects will be asked to bring in their used study pens and the pen that they are using so that study nurse can log in the amount of drug used. Blood glucose concentrations will be reviewed. Insulin dose will be adjusted if needed. Study drug will be dispensed for additional 4 weeks.

Study visit week 24: CGM will be inserted. They will have their body composition measured by DEXA and MRI prior to next visit.

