Study Visit week 26: Subjects will come fasting for this visit. Research labs, CBC, CMP, Lipids, HbA1c and fructosamine will be collected. Records of blood glucose concentrations monitored by finger-stick and CGM for the previous 14 days will be obtained to assess their glycemic control. They will undergo meal challenge test (described above) and a fat biopsy. 24 hr urine will be collected. FMD and 24hr blood pressure will be performed. After this visit, subjects will be discharged from the study.

Blood samples (collected in protease and DPP-IV inhibitors) will be appropriately processed and assayed for glucose, C-peptide, glucagon, GLP-1 and gastric inhibitory peptide (GIP) which is also called gastric insulinotropic peptide, Reactive oxygen species (ROS) generation, Thiobarbituric acid reducing substances (TBARS), urinary isoprostanate,

intranuclear nuclear factor kappa B (NFkB) binding, the expression and concentration of Toll like receptor-4 (TLR-4), tumor necrosis factor alpha (TNF α), Inhibitor kappa B (IkB α), Matrix metalloproteinase 9 (MMP-9), Suppressor of cytokine signaling-3 (SOCS-3), Protein kinase C (PKC β II), Phosphotyrosine phosphatase -1B (PTP-1B), Glycogen synthase kinase 3 beta (GSK-3 β), Inhibitor kappa kinase (IKK β), C-jun amino terminal kinase (JNK-1) and amount of Insulin receptor (IR- β) and p-IR β in MNC and plasma concentrations of C-reactive protein (CRP), Monocyte chemoattractant protein -1 (MCP-1), Plasminogen activator inhibitor -1 (PAI-1), TNF α and Regulated upon activation Normal T cell Expressed and Secreted (RANTES). Adipose tissue samples will be processed and analyzed for intranuclear NFkB binding, the expression and concentration of TLR-4, TNF α , IkB α , MMP-9, SOCS-3, PKC β II, PTP-1B, GSK-3 β , IKK β , JNK-1 and amount of IR- β and p-IR β .

Clinical and Laboratory Procedures

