17.0 Data Management and Analysis

17.1 Describe the data analysis plan, including any statistical procedures. This section applies to both quantitative and qualitative analysis.

Response: The focus of the proposed research is to evaluate the effect of liraglutide on mean HbA1c% over the period of 26 weeks of treatment. The similarities between the study groups, baseline values for subject's demographics and study endpoints will be compared using appropriate parametric tests. Transformations of the data in order to meet statistical assumptions may be considered. The **primary endpoint** of the study is to detect

a difference in HbA1c after 26 weeks of treatment with Liraglutide or placebo. The statistical analysis will be carried out using analysis of covariance (ANCOVA) and tested at the 0.05 level. Change in weight will be a covariate. The results will be computed as mean \pm SD. Analysis will be carried out on the basis of intention to treat (with last observation carried forward).

The secondary end points based on glycemic changes will include the difference from baseline in mean weekly glucose concentrations, standard deviations of the mean weekly glucose concentrations, HbA1c, fructosamine, the duration of time spent in hyperglycemia ($>150\text{mg/dl}$, $>200\text{mg/dl}$, $>250\text{mg/dl}$) and hypoglycemia ($<70\text{mg/dl}$, $<40\text{mg/dl}$), insulin dosage. A reduction in the AUC following the meal will constitute another secondary end point. Between groups comparisons of the magnitude of change from baseline will also be made for these glycemia related secondary endpoints using student's t-test. Comparisons for these and the primary endpoints will also be made using the paired t-test or Wilcoxon's test for paired data within each group.

The other secondary end-points of the study will be change from baseline after 26 weeks of treatment in the fasting and postprandial blood sugars, glucagon and C-peptide concentrations, indices of oxidative and inflammatory stress in MNC, plasma and adipose tissue; subcutaneous fat mass, hepatic fat content and visceral fat mass; features of metabolic syndrome; gastric emptying, blood pressure, vascular analysis, patient reported nausea, quality of life and depression scores. Between groups comparisons will be made using students t-test or ANCOVA (adjustment will be done for baseline differences). Within group comparisons for these endpoints will be made using paired t-test or Wilcoxon's test or ANCOVA.

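### Week 12 values of HbA1c, fructosamine, lipids, research labs, 24-hour urine, FMD and 24-hour blood pressure have no stated role in the section 17.1 analysis except as carried-forward substitutes for week 26.

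*Combined protocol and SAP*

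**What the plan says.** **Schedule (section 10.1).** The week 12 visit includes fasting blood and research labs, and "HbA1c, fructosamine, lipid panel, urine pregnancy test and 24 hr urine will be collected. FMD and 24hr blood pressure will be studied". The same measures return at week 26: "Research labs, CBC, CMP, Lipids, HbA1c and fructosamine will be collected" and "FMD and 24hr blood pressure will be performed", together with a 24-hour urine. Baseline counterparts exist. HbA1c and lipids are taken at screening. FMD, 24-hour urine and ambulatory pressure are taken on day -1 ("The subjects will have their 24 hour blood pressure measurements completed"). Fructosamine is taken on day 0 ("A fructosamine and blood samples will be collected at baseline").

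**Analysis (section 17.1).** The primary endpoint is HbA1c after 26 weeks, by ANCOVA, intention to treat with LOCF. A second paragraph lists glycemic secondaries, HbA1c and fructosamine among them, as differences from baseline tested by t-test, and gives no visit. A third paragraph covers the stress and inflammation markers, metabolic-syndrome features, blood pressure and vascular measures: "The other secondary end-points of the study will be change from baseline after 26 weeks of treatment". These are tested by t-test or ANCOVA.

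**Aims (section 1.2).** Aim 1.1 places HbA1c and fructosamine before and after 26 weeks of treatment. Aim 6.2 does the same for the vascular measure: "measuring flow mediated dilatation (FMD) in brachial artery before and 26 weeks after treatment with liraglutide".

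**The concern.** Each of these endpoints has one baseline and two on-treatment values, and the plan says how to analyse only one of the two. Three things follow.

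- Where week 26 is missing and LOCF applies, the week 12 result is treated as if observed at week 26.
- The LOCF sentence stands in the primary-endpoint paragraph, so its reach to FMD, blood pressure and the markers is unclear. Section 20.3 lets patients drop single procedures while staying on study drug, so gaps in one endpoint at week 26 are foreseeable.
- For the glycemic secondaries, section 17.1 itself names no visit. A reader must go to Aim 1.1 to learn that week 26 is meant.

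At stake are some precision, a clean week 26 estimate, and protection against choosing the visit after the data are seen. The endpoints affected are HbA1c, fructosamine, lipids, blood pressure, FMD and the blood and urine markers. Fat mass, adipose-tissue markers, meal-test and CGM endpoints are not affected, because week 12 does not measure them.

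**Working it through.** **1. The plan's own figure.** Section 17.2 gives 32 per group for a difference of 0.35, residual SD 0.5, 80% power and alpha 0.05. Two-sided: n = 2 × [0.5 × (1.960 + 0.842) / 0.35]² = 32.04 per group, which reproduces the 32. No power or SD is given for any secondary endpoint.

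**2. Precision for the week 26 contrast.** Let *c* be the fraction of patients with both visits, *m* the fraction with week 12 only, and *r* the baseline-adjusted correlation between weeks 12 and 26. Relative to ANCOVA on week 26 completers, a repeated-measures model reduces the variance by the fraction

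r² × m / (c + m).

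The documents give none of these three quantities. Assume c = 0.70 (in line with the planned 30% dropout), m = 0.15 and r from 0.3 to 0.7. Then m / (c + m) = 0.15 / 0.85 = 0.176.

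| r | Variance reduction at week 26 |
|---|---|
| 0.3 | 0.09 × 0.176 = 1.6% |
| 0.5 | 0.25 × 0.176 = 4.4% |
| 0.7 | 0.49 × 0.176 = 8.6% |

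A second parameterisation starts from an equal raw correlation of 0.3 to 0.8 between all visits. The adjusted correlation is then r / (1 + r) = 0.23 to 0.44. With 30% missing at week 26, and half or all of those having week 12 data, the reduction is about 1% to 6%. If nobody has week 12 only, it is zero.

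**3. What LOCF does under the same assumptions.** Of patients with at least a week 12 value, 17.6% contribute that value as their week 26 result. If the week 12 effect were half the week 26 effect, the LOCF estimate in this group would be 1 − 0.176 × 0.5 = 91% of the week 26 effect. If the two effects were equal, this attenuation would be zero.

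**4. Averaging weeks 12 and 26 instead.** The average has variance (1 + r) / 2 of a single visit. Take an illustrative effect of 0.5 SD at week 26 and 32 per arm (two-sided t-test, alpha 0.05). Week 26 alone has 50% power.

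| r | Variance ratio | Power, equal effects | Power, week 12 effect half | Break-even week 12 effect |
|---|---|---|---|---|
| 0.3 | 0.65 | 69% | 45% | 61% |
| 0.5 | 0.75 | 62% | 40% | 73% |
| 0.7 | 0.85 | 57% | 36% | 84% |

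Break-even is the week 12 effect, as a share of the week 26 effect, at which the average matches week 26 alone: 2 × √[(1 + r) / 2] − 1.

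**The case against.** The strongest reply is that testing one landmark visit and keeping an intermediate visit for LOCF or description is a legitimate design. It need not bias the result for patients who have week 26 data, and the loss for the stated question is small. That stands: section 2 of the working puts it in single-digit percentages. The group with week 12 but not week 26 data may also be smaller than the assumed 15%, because the nausea withdrawals set out in section 10.1 fall at weeks 1 and 2.

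A reader might infer that the week 12 data go unused. The documents do not support that, because LOCF brings them in for patients lost after week 12. A reader might also infer that section 17.1 confines every endpoint to 26 weeks. For HbA1c and fructosamine in the glycemic list it names no visit, and the limit comes from Aim 1.1.

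A third tempting inference is a large gain in power, from 50% to between 57% and 69%. That applies to the two-visit average with equal effects, which is not the question the aims ask. With half the effect at week 12, power falls to between 36% and 45%, below week 26 alone. Nor do the documents give any variability figure that would show FMD or ambulatory pressure to be especially noisy.

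The reply does not answer two things: LOCF counts a week 12 value as a week 26 value, and it adds nothing for patients who have both.

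**Conclusion.** The concern holds as a gap in specification that is cheap to close. Section 17.1 gives the week 12 values no role beyond LOCF substitution, and for FMD, blood pressure and the markers even that role is uncertain. The precision to be gained at week 26 is about 2% to 9% of variance, resting on an assumed adjusted correlation of 0.3 to 0.7 and an assumed 15% of patients with week 12 only. The stronger reasons to act are that week 26 estimates should not contain week 12 values in disguise, and that the visit tested should be settled before the data are seen. The documents do not support a claim of a substantial loss of power for the week 26 question.

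**What to change.** In section 17.1, for each endpoint measured at baseline, week 12 and week 26, replace the t-test or ANCOVA with LOCF by one baseline-adjusted repeated-measures model. Its terms are treatment, visit, treatment-by-visit and baseline-by-visit, with unstructured covariance. Name the week 26 contrast as the main result and pre-specify the week 12 contrast as secondary. State week 26 explicitly for the glycemic secondaries.

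An average of weeks 12 and 26 is optional. If included, label it supportive: it estimates a different quantity, and it gains power only if the week 12 effect is at least about 61% to 84% of the week 26 effect.

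The cost is revised wording and slightly more analysis, with no new data. The model relies on data being missing at random. Whether weight change stays as a covariate for HbA1c is a separate question that this change does not settle.

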11.0 Study Timelines

11.1 Describe the anticipated duration needed to enroll all study subjects.

Response: 48 months

11.2 Describe the duration of an individual subject's participation in the study. Include length of study visits, and overall study follow-up time.

Response: After the screening visit, subjects who meet the inclusion and exclusion criteria, will be assigned a number and randomized to receive subcutaneous injection daily of either Liraglutide (42 subjects) or placebo (42 subjects) for 26 weeks. Total participation period will be 28 weeks including 2 weeks run in period before starting drug intervention.

11.3 Describe the estimated duration for the investigators to complete this study (i.e. all data is collected and all analyses have been completed).

Response: 60 months

12.0 Setting

12.1 Describe all facilities/sites where you will be conducting research procedures. Include a description of the security and privacy of the facilities (e.g. locked facility, limited access, privacy barriers). Facility, department, and type of room are relevant. Do not abbreviate facility names.

NOTE: Examples of acceptable response may be: "A classroom setting in the Department of Psychology equipped with a computer with relevant survey administration software," "The angiogram suite at Buffalo General Medical Center, a fully accredited tertiary care institution within New York State with badge access," or, "Community Center meeting hall."

Response: Research will be conducted at the Diabetes Endocrinology Research Center of WNY, located at [name] and at the CTRC located in [name]. The Diabetes Research Center has facilities and exam rooms available for insulin pump download, CGM device download, meal and infusion studies and presence of

study coordinator and registered nurse for data collection and blood work at all times. One of the investigators will be available at all times to address patients' related issues. CTRC location is a fully equipped laboratory with equipment include ultra-low freezers for sample storage, centrifuges, microscopes for sample preparation, infusion pumps, ELISA, PCR and immunoblotting instrumentation.

12.2 For research conducted outside of UB and its affiliates, describe:

- Site-specific regulations or customs affecting the research
- Local scientific and ethical review structure

NOTE: This question is referring to UB affiliated research taking place outside UB, i.e. research conducted in the community, school-based research, international research, etc. It is not referring to multi-site research. UB affiliated institutions include Kaleida Health, ECMC, and Roswell Park Cancer Institute.

Response:

N/A: This study is not conducted outside of UB or its affiliates.

13.0 Community-Based Participatory Research

13.1 Describe involvement of the community in the design and conduct of the research.

NOTE: Community-Based Participatory Research (CBPR) is a collaborative approach to research that equitably involves all partners in the research process and recognizes the unique strengths that each brings. CBPR begins with a research topic of importance to the community, has the aim of combining knowledge with action and achieving social change to improve health outcomes and eliminate health disparities.

Response:

N/A: This study does not utilize CBPR.

13.2 Describe the composition and involvement of a community advisory board.

Response:

N/A: This study does not have a community advisory board.

